Adverse events reported on trametinib dimethyl sulfoxide (GSK1120212B) trials, but for which there is insufficient evidence to suggest that there was a reasonable possibility that trametinib dimethyl sulfoxide (GSK1120212B) caused the adverse event:

BLOOD AND LYMPHATIC SYSTEM DISORDERS - Disseminated intravascular coagulation; Febrile neutropenia; Leukocytosis

CARDIAC DISORDERS - Atrial fibrillation; Cardiac arrest; Myocardial infarction; Restrictive cardiomyopathy; Sinus tachycardia

EYE DISORDERS - Corneal ulcer; Eyelid function disorder; Flashing lights; Floaters; Glaucoma; Photophobia

GASTROINTESTINAL DISORDERS - Ascites; Duodenal ulcer; Esophageal necrosis; Esophageal ulcer; Esophagitis; Gastric hemorrhage⁷; Gastric ulcer; Gastritis; Gastrointestinal disorders - Other (intestinal obstruction); Gastrointestinal disorders - Other (pneumatosis intestinalis); Gastrointestinal fistula; Gingival pain; Hemorrhoidal hemorrhage⁷; Ileus; Obstruction gastric; Pancreatitis; Small intestinal obstruction

GENERAL DISORDERS AND ADMINISTRATION SITE CONDITIONS - Flu like symptoms; General disorders and administration site conditions - Other (axillary pain); Localized edema; Malaise; Non-cardiac chest pain; Pain

HEPATOBILIARY DISORDERS - Cholecystitis; Hepatic failure; Hepatic pain; Hepatobiliary disorders - Other (hepatic encephalopathy)

INFECTIONS AND INFESTATIONS - Biliary tract infection; Catheter related infection; Device related infection; Endocarditis infective; Enterocolitis infectious; Hepatitis viral; Infections and infestations - Other (abscess limb); Infections and infestations - Other (necrotizing fasciitis); Infections and infestations - Other (oral infection); Pharyngitis; Sepsis; Upper respiratory infection; Urinary tract infection

INJURY, POISONING AND PROCEDURAL COMPLICATIONS - Bruising

INVESTIGATIONS - Blood bilirubin increased; Blood lactate dehydrogenase increased; Creatinine increased; Electrocardiogram QT corrected interval prolonged; GGT increased; Lipase increased; Lymphocyte count decreased; Platelet count decreased; Serum amylase increased; White blood cell decreased

METABOLISM AND NUTRITION DISORDERS - Hyperglycemia; Hyperkalemia; Hyperphosphatemia; Hyperuricemia; Hypocalcemia; Hypoglycemia; Hypokalemia

MUSCULOSKELETAL AND CONNECTIVE TISSUE DISORDERS - Generalized muscle weakness; Muscle cramp; Musculoskeletal and connective tissue disorder - Other (compression fracture); Myalgia; Neck pain

NEOPLASMS BENIGN, MALIGNANT AND UNSPECIFIED (INCL CYSTS AND POLYPS) - Tumor hemorrhage⁷; Tumor pain

NERVOUS SYSTEM DISORDERS - Dysgeusia; Encephalopathy; Intracranial hemorrhage⁷; Lethargy; Nervous system disorders - Other (diplopia); Seizure; Somnolence; Stroke; Syncope; Transient ischemic attacks

PSYCHIATRIC DISORDERS - Anxiety; Confusion; Delirium; Depression; Hallucinations; Insomnia; Personality change

RENAL AND URINARY DISORDERS - Acute kidney injury; Cystitis noninfective; Dysuria; Hematuria; Proteinuria; Urinary incontinence

REPRODUCTIVE SYSTEM AND BREAST DISORDERS - Vaginal fistula; Vaginal hemorrhage⁷

RESPIRATORY, THORACIC AND MEDIASTINAL DISORDERS - Bronchopulmonary hemorrhage⁷; Hypoxia; Laryngeal edema; Oropharyngeal pain; Pleural effusion; Pneumothorax; Productive cough; Pulmonary hypertension; Respiratory failure; Sinus disorder

SKIN AND SUBCUTANEOUS TISSUE DISORDERS - Bullous dermatitis; Photosensitivity; Purpura; Skin and subcutaneous tissue disorders - Other (erythema nodosum); Skin ulceration; Urticaria

VASCULAR DISORDERS - Hematoma; Hot flashes; Hypotension

NOTE: Trametinib (GSK1120212B) in combination with other agents could cause an exacerbation of any adverse event currently known to be caused by the other agent, or the combination may result in events never previously associated with either agent.

5.4 Dose Modifications

5.4.1 General Instructions

5.4.1.1 Dabrafenib/Trametinib Dose Reduction Procedures

- If treatment related toxicities occur when dabrafenib and trametinib are used in combination, then both

agents should be simultaneously dose reduced, interrupted or discontinued with the exception of the following:

- Dose modifications are required for dabrafenib only (and not trametinib) for these events: pyrexia and, RAS mutation positive non-cutaneous malignancies
- Dose modifications are required for trametinib only (and not dabrafenib) for these events: left ventricular rejection fraction (LVEF) reduction, retinal vein occlusion (RVO) retinal pigment epithelial detachment (RPED) and interstitial lung disease (ILD)/pneumonitis (primarily related to trametinib).

NOTE: Dose modifications are not recommended for adverse reactions of cutaneous squamous cell carcinoma (cuSCC) or new primary melanoma.

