4.5 Emergency Unblinding

The information provided below is for the use by a physician, nurse, CRA or pharmacist treating the patient. These contact numbers should not be used by patients. Patients should be instructed to call their doctor's office

in the event of an emergency or adverse event that may result in the need to unblind the patient.

In the event of an emergency or severe adverse reaction necessitating identification of the medication for the welfare of the patient, please contact the EA Drug Team at [contact] during business hours (9am-4pm M-F Eastern Time) or AnswerConnect at [name] outside of those hours. The request will require the protocol number (i.e., EA6191), the patient ID number (5-digit number), patient initials, patient step, your contact information, as well as the reason for unblinding. ECOG-ACRIN staff may contact you for further details in order to determine the validity of the request, and will work to obtain the required approvals to unblind the patient. Once approved, a staff member will provide the unblinded treatment identity. Note that if a patient is unblinded, they must discontinue protocol treatment.

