LVEF Changes: If any of the following circumstances occur, the event(s) must be reported via CTEP-AERS within 7 calendar days

- Asymptomatic: Absolute decrease of >10% in LVEF compared to baseline and ejection fraction below the institution's LLN that does not resolve within 4 weeks (i.e.: defined as LVEF \geq LLN and absolute decrease \leq 10% compared to baseline)
- Symptomatic: Grade 3-4 LVEF

Please refer to the dose modification instructions for further information regarding Treatment Modification and Management Guidelines for LVEF Decrease.

Visual Changes: If RPED (retinal pigment epithelial detachments) is suspected or diagnosed or RVO (retinal vein occlusion) is diagnosed, the event(s) must be reported via

CTEP-AERS within 7 calendar days. Please refer to the dose modification instructions for further information regarding Treatment Modification and Management Guidelines for Visual Changes.

Pyrexia: Any occurrence of pyrexia accompanied by hypotension, or dehydration requiring IV fluids, or severe rigors/chills in the absence of an obvious infectious must be reported via CTEP-AERS within 7 calendar days.

Liver Chemistry Changes: If any of the following circumstances occur, the event(s) must be reported via CTEP-AERS within 7 calendar days

- ALT \geq 3xULN and bilirubin \geq 2x ULN or $>$ 35% direct bilirubin
- ALT \geq 3xULN and INR \geq 1.5, if INR measured (INR threshold does not apply if patient is on anticoagulant)
- ALT $>$ 5xULN
- ALT $>$ 3xULN persistent for $>$ 4 weeks
- ALT $>$ 3xULN associated with symptoms (new or worsening) believed to be related to liver injury or hypersensitivity

Please refer to the dose modification instructions for further information regarding Treatment Modification and Management Guidelines for Liver Chemistry Changes.

c. NOTE: All adverse events meeting the criteria in this table that occurs while the patient is on study treatment and for 30 days after the last dose of protocol treatment must be reported in CTEP-AERs according to the timeframes outlined. Any adverse event meeting the criteria that occurs more than 30 days after the last dose of protocol treatment and is related to Hydroxychloroquine/Placebo must be reported in CTEP-AERS according to the timeframes outlined.

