5.4.2 General Guidelines for Toxicities and Dose Modifications

Guidelines for specific toxicities are outlined below, but general guidelines for toxicities not listed are provided in Table 5.

Table 4: General Dose modification guidelines for dabrafenib and trametinib for toxicities attributable to only dabrafenib and/or trametinib. These are general guidelines but for specific toxicities dose modification instructions may be different and are provided in the subsequent sections.

CTCAE Grade	Action and Dose Modification
Grade 1	
 Continue dabrafenib, trametinib and HCQ/placebo at current dose level Monitor closely

CTCAE Grade	Action and Dose Modification
	
 Provide supportive care according to institutional standards
Grade 2	
 Interrupt dabrafenib and trametinib if clinically indicated, continue HCQ/placebo Monitor closely Provide supportive care according to institutional standards When toxicity resolves to Grade 1 or baseline, restart dabrafenib and trametinib treatment at current dose level
Grade 3	
 Interrupt dabrafenib and trametinib if clinically indicated, continue HCQ/placebo Monitor closely Provide supportive care according to institutional standards When toxicity resolves to Grade 1 or baseline, restart dabrafenib and trametinib both reduced by one dose level If the Grade 3 toxicity recurs, interrupt study treatment When toxicity resolves to Grade 1 or baseline, restart dabrafenib and trametinib both reduced by another dose level
Grade 4	
 Interrupt dabrafenib and trametinib, continue HCQ/placebo Monitor closely Provide supportive care according to institutional standards If event resolves to Grade 1 or baseline patient may continue dabrafenib and trametinib both reduced by one dose level If event does not resolve permanently discontinue study treatment

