Decreases in left ventricular ejection fraction have been seen with the use of trametinib with an incidence of 9% with the combination of trametinib and dabrafenib compared to 0% with dabrafenib alone. Therefore, transthoracic echo must be performed at baseline and repeated every 3 months while on study or as clinically indicated. More frequent evaluation is warranted if there are signs or symptoms suggestive of clinical CHF. The same procedure (either ECHO or MUGA, although ECHO

is preferred) should be performed at baseline and at follow-up visit(s).

Table 10: Management and Dose Modification Guidelines of Trametinib for LVEF Decrease

Clinic	LVEF-drop (%) or CTCAE grade	Action and Dose Modification
Asymptomatic	Absolute decrease of > 10% in LVEF compared to baseline and ejection fraction below the institution's LLN	
Interrupt trametinib and repeat ECHO within 2 weeks^{a,b}
 
If the LVEF recovers within 4 weeks (defined as LVEF \geqLLN and absolute decrease \leq10% compared to baseline) then restart at a reduced dose level of trametinib.
 
 Repeat ECHO at 2, 4, 8 and 12 weeks after re-start; continue in intervals of 12 weeks thereafter 
If LVEF does not recover within 4 weeks
 
 Consult with cardiologist Permanently discontinue trametinib Report as SAE Repeat ECHO after 2, 4, 8, 12, and 16 weeks or until resolution
Symptomatic ^b	Grade 3: resting LVEF 39-20% or >20% absolute reduction from baseline	
Permanently discontinue trametinib
 
Report as SAE
 
Interrupt dabrafenib.^c
 
Consult with cardiologist
 
Repeat ECHO after 2, 4, 8, 12, and 16 weeks or until resolution
 
Grade 4 toxicity will trigger unblinding per Section 4.5

	Grade 4: resting LVEF < 20%	

- If ECHO does not show LVEF recovery after 2 weeks, repeat ECHO 2 weeks later.
- Symptoms may include: dyspnea, orthopnea, and other signs and symptoms of pulmonary congestion and edema.
- Once LVEF recovers, including resolution of symptoms, restart of dabrafenib monotherapy will be at the discretion of the study investigator.

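### Section 5.4.1.1 rules out any dabrafenib change for LVEF reduction, but Table 10 interrupts dabrafenib for symptomatic grade 3-4 LVEF decrease (minor)

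*Combined protocol and SAP*

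**What the plan says.** - **Section 5.4.1.1.** By default, a treatment-related toxicity leads to the same action on dabrafenib and trametinib, whether that is reduction, interruption or discontinuation. Exceptions follow, among them: "Dose modifications are required for trametinib only (and not dabrafenib) for these events: left ventricular rejection fraction (LVEF) reduction". Neither grade nor symptoms limit this exception.
- **Section 5.4.3.6, Table 10.** The caption is "Table 10: Management and Dose Modification Guidelines of Trametinib for LVEF Decrease". The asymptomatic row acts on trametinib alone. The symptomatic row, which covers grades 3 and 4, discontinues trametinib permanently and adds "Interrupt dabrafenib". Its footnote c leaves a restart of dabrafenib monotherapy, once LVEF and symptoms have recovered, to the investigator. The same row says "Grade 4 toxicity will trigger unblinding per Section" 4.5.
- **Section 4.5.** "Note that if a patient is unblinded, they must discontinue protocol treatment".
- **Section 5.2.8.** The expedited-reporting list includes "Symptomatic: Grade 3-4 LVEF", followed by "Please refer to the dose modification instructions for further information regarding Treatment Modification and Management Guidelines for LVEF Decrease".
- **Section 5.4.2.** Specific toxicities are said to be covered below, and the sentence continues: "general guidelines for toxicities not listed are provided in Table 5". Table 5 is the dabrafenib-only pyrexia table. The general guideline is Table 4, printed directly under that sentence.

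**The concern.** Two operative instructions disagree for the same patient. For a symptomatic grade 3 LVEF decrease, Section 5.4.1.1 excludes a change to dabrafenib and Table 10 requires one. Section 5.4.1.1 is not merely a general statement on this point: it names LVEF and names dabrafenib as the drug to leave alone. A site that read only that section would continue dabrafenib in a patient with symptomatic cardiac dysfunction whom Table 10 takes off the drug, at least until recovery. The event is serious, since it calls for expedited reporting and permanent discontinuation of trametinib. At stake is patient management. The design and the analysis are not involved.

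**Working it through.** **1. The texts side by side.**

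| LVEF decrease | Section 5.4.1.1, dabrafenib | Table 10, dabrafenib | Agreement |
|---|---|---|---|
| Asymptomatic | not modified | no action listed | yes |
| Symptomatic grade 3 | not modified | interrupted | **no** |
| Symptomatic grade 4 | not modified | interrupted; unblinding triggered | no, but settled by Section 4.5 |

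**2. Does interruption count as a dose modification?** Yes. The sentence in Section 5.4.1.1 that introduces the exceptions covers interruption as well as reduction and discontinuation. Table 10 lists the interruption in its column for actions and dose modifications. The two texts therefore concern the same kind of action.

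**3. Which text is the mistaken one?** Footnote c of Table 10 provides for restarting dabrafenib, so the interruption is deliberate. The other events in the same exception list fit Section 5.4.1.1: Table 9 (pneumonitis) acts on trametinib only, and Tables 13 and 14 (RVO and RPED) order no dabrafenib change. Only the symptomatic LVEF row departs from the list. The list needs the correction.

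**4. Where does the conflict matter in practice?** At grade 4, Table 10 triggers unblinding, and Section 4.5 then requires protocol treatment to stop, so dabrafenib stops as protocol treatment in any case. That leaves mainly symptomatic grade 3.

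**5. How many patients?**

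- Planned accrual is 84 (Section 9.3).
- Grade 3 ejection fraction decrease was 1 patient (4%) in BAMM and 4% in the doublet comparator (Section 1.1.4, Table 3). The percentages in that table imply a BAMM denominator of 25: 14/25 = 56%, 13/25 = 52%, 1/25 = 4%.
- Expected grade 3 cases over both arms: 84 × 0.04 = 3.36, about 3.
- The documents do not give the symptomatic share. Under assumed shares the expected number is:

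| Assumed symptomatic share | Patients meeting the conflict |
|---|---|
| 0% | 0 |
| 25% | 3.36 × 0.25 = 0.84 |
| 50% | 3.36 × 0.50 = 1.68 |
| 100% | 3.36 |

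Section 1.1.6 mentions one BAMM patient who stayed on the BRAF inhibitor and HCQ after an echocardiogram showed a reduced ejection fraction. It does not say whether this was the grade 3 case or whether there were symptoms, so a share of zero is possible.

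**6. Check against the any-grade rate.** On dabrafenib plus trametinib, LVEF decrease of any grade is given as 8% (Section 1.1.4, Table 3) or 9% (Section 5.4.3.6). That is 84 × 0.08 = 6.72 to 84 × 0.09 = 7.56 patients. About 3 grade 3 cases is compatible with this.

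**7. The table number in Section 5.4.2.** Taken literally, Table 5 would send an unlisted toxicity to the pyrexia rules, which interrupt dabrafenib and continue trametinib. Section 5.4.1.3 cites Table 4 correctly, and Table 4 follows directly after the faulty reference. This is a clerical slip.

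**The case against.** The strongest reply is that the protocol already guides the reader to Table 10.

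- Section 5.4.1 is headed as general instructions and Section 5.4.3 as guidance for specific toxicities.
- The opening sentence of Section 5.4.2 sends listed toxicities to the later sections, and LVEF is listed there.
- Section 5.4.1.3, within the general part itself, refers non-hematological toxicities attributed to trametinib to the modifications that follow.
- The caption of Table 4 says that specific instructions may differ from the general ones.
- Section 5.2.8 names symptomatic grade 3-4 LVEF as an expedited event and refers to management guidelines whose name matches the caption of Table 10.

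Most of this stands. On an ordinary reading Table 10 governs, and it is also the more cautious instruction, so most sites would follow it. A reader might infer that sites have no means of telling which instruction applies. The documents do not support that.

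What does not stand is that the conflict is thereby removed. None of these passages states that Table 10 overrides the explicit exclusion in Section 5.4.1.1. The remark about differing instructions qualifies Table 4, not the exception list. The caption of Table 10 itself names trametinib only, so it gives no warning of an action on dabrafenib.

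**Conclusion.** The inconsistency is real and minor. Section 5.4.1.1 is wrong as written for symptomatic grade 3-4 LVEF decrease, and the case left open in practice is mainly symptomatic grade 3. At a 4% grade 3 rate, about 3 of 84 patients would have the event, and between none and all of them would be symptomatic. This assumes that the 4% seen in BAMM and in the doublet comparator carries over to this population.

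Three stronger readings are not supported.

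- A reader might take the exact 95% confidence limits for 1/25 (0.1% to 20.4%) and arrive at as many as 84 × 0.2035 = 17.1 patients. That would put symptomatic grade 3 decrease alone at about one patient in five, against 8% to 9% for any grade on the doublet. Those figures exclude HCQ, which could add some cases, but nothing in the documents suggests an increase of that size.
- A reader might infer an effect on the trial's result. The instructions are the same in both blinded arms, and neither the one-year PFS comparison nor its sample size depends on them. Bias, power and type I error are not affected.
- A reader might take the wrong table number as a sign of wider unsafe guidance. The right table is printed directly beneath the reference, and the slip adds no weight to the LVEF point.

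**What to change.** In Section 5.4.1.1, add to the LVEF exception: *except symptomatic grade 3-4 LVEF decrease, for which dabrafenib is also interrupted; see Table 10*. Alternatively, state there that the toxicity-specific tables in Section 5.4.3 govern where they differ. Either edit is sufficient alone.

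In Section 5.4.2, change Table 5 to Table 4, as an editorial correction.

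The cost is one clause or sentence and one table number, which can go into the next protocol amendment. Design, data collection and analysis stay as they are.

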5.4.1.2 Dose Level Reduction Tables

Table 1: Dabrafenib Dose Level Reductions

Dose Level	Dose/Schedule
Starting Dose	150 mg twice daily
First Reduction	100 mg twice daily
Second Reduction	75 mg twice daily
Third Reduction	50 mg twice daily
If unable to tolerate 50 mg twice daily	Discontinue dabrafenib

Trametinib Dose Reductions

Table 2: Trametinib Dose Reductions

Dose Level	Dose/Schedule
Starting Dose	2 mg twice daily
First Reduction	1.5 mg twice daily
Second Reduction	1.0 mg twice daily
Third Reduction	0.5 mg twice daily
If unable to tolerate 0.5 mg once daily	Discontinue trametinib

Hydroxychloroquine/Placebo Dose Reductions

Table 3: HCQ/placebo Dose Reductions

Dose Level	Dose/Schedule
Starting Dose	600 mg twice daily
First Reduction	600 mg once daily in the morning and

Dose Level	Dose/Schedule
	400 mg once daily in the evening
Second Reduction	400 mg twice daily
Third Reduction	A third dose reduction to 400 mg once a day (qd) may be pursued in patients deemed to be deriving clinical benefit at the discretion of the treating physician.

For any AE with a grade ≥ 3 , HCQ/placebo dose will be held until the toxicity resolves to \leq grade 1 before restarting, after which HCQ/placebo may be restarted at a reduced dose as described in table 3.

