1.1.3 Phase I dose escalation

Six patients were enrolled on the phase I dose escalation portion of the BAMM study. No DLTs were reported. The recommended phase II dose of HCQ 600 mg po bid combined with dabrafenib 150 mg po bid and trametinib 2 mg po qd was used for the single arm phase II study. All patients in the phase I and II portions of the study were assessed for response and toxicity below.

Response

The investigator assessed best overall response rate for the study population was 85% (Table 2). The complete response rate was 41%. Below we provide post-hoc exploratory subgroup analyses of this single arms study. The best overall response rate for patients with elevated LDH (88%), prior therapy (83%), and baseline tumor size ≥ 5

cm (89%), and the complete response rate in elevated LDH (25%), prior therapy (39%), and baseline tumor size ≥ 5 cm (33%) suggests this regimen is effective at eliciting response in the most aggressive Stage IV *BRAF* mutant melanoma patients. Waterfall plots for the overall population and these subgroups demonstrates this further (Figure 1).

Table 2. Response Rates

Response	Investigator Assessed	Rad. Core Assessed*	LDH \leq ULN	LDH $>$ ULN	No prior therapy	Prior therapy	BTS $<$ 5 cm	BTS \geq 5 cm
CR	14/34 (41%)		10/18 (56%)	4/16 (25%)	7/16 (44%)	7/18 (39%)	8/16 (50%)	6/18 (33%)
PR	15/34 (46%)		5/18 (27%)	10/16 (63%)	7/16 (44%)	8/18 (44%)	5/16 (31%)	10/18 (56%)
SD	3 (8%)		2/18 (11%)	1/16 (6%)	2/16 (12%)	1/18 (6%)	2/16 (13%)	1/18 (6%)
PD	2 (5%)		1/18 (6%)	1/16 (6%)	0	2/18 (11%)	1/16 (6%)	1/18 (5%)
N	34		18	16	16	18	16	18
BORR	29/34 (85%)		15/18 (83%)	14/16 (88%)	14/16 (88%)	15/18 (83%)	14/16 (81%)	16/18 (89%)

*In process; CR: complete response; PR: partial response; SD: stable disease; PD: progressive disease; BORR: Best Overall Response Rate; LDH: lactate dehydrogenase; ULN: upper limit of normal; BTS: Baseline Tumor Size

[figure not shown]

Fig. 1 Waterfall Plots for Maximum change in Target lesions. Overall study population B. According to LDH status C. According to prior therapy D. According to Baseline tumor size as determined by the sum of the RECIST target lesions on baseline scans

Rev Add2

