5.1.1 Arm A

- Dabrafenib 150 mg by mouth (PO) twice daily (BID)
- Trametinib 2 mg by mouth (PO) once daily (QD)
- Hydroxychloroquine (HCQ) 3 pills by mouth (PO) twice daily (BID)

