5.1.3 Dabrafenib and Trametinib administration

The starting dose for dabrafenib is 150 mg BID. Capsules of dabrafenib are available in 50 mg and 75 mg strength doses. Dabrafenib will be administered twice daily approximately twelve hours apart on an empty stomach – either one (1) hour before meals or two (2) hours after. Patients will be instructed to swallow the whole capsules in rapid succession without chewing. If a dose is missed, it should not be taken if it is less than 6 hours until the next dose.

The starting dose of trametinib is 2 mg daily. Tablets of trametinib are available in 0.5 mg and 2 mg strength. Trametinib will be administered once daily on an empty stomach – either one (1) hour before meals or two (2) hours after. Patients will be instructed to swallow the whole tablet without chewing. If a dose of trametinib is missed, the dose can be taken if it is more than 12 hours until the next scheduled dose.

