Appendix III

Patient Pill Calendar

Pill Calendar Directions

1. Take your scheduled dose of each pill.
 - Dabrafenib should be taken twice daily, about 12 hours apart on an empty stomach (1 hour before or 2 hours after meals)
 - Trametinib should be taken once daily, on an empty stomach (1 hour before or 2 hours after a meal)
 - Hydroxychloroquine (HCQ or placebo) should be taken twice daily, about 12 hours apart (in the morning and evening). It can be taken with or without food.
2. If you forget, the missed pills will not be taken later.
3. Please bring the empty bottles or any leftover capsules/ tablets and your pill calendar to your next clinic visit.

Patient Pill Calendar

This is a calendar on which you are to record the time and number of tablets you take each day. You should take your scheduled dose of each pill. **Note the times and the number of tablets that you take each day.** If you develop any side effects, please record them and anything you would like to tell the doctor in the space provided. Bring any unused tablets and your completed pill calendar to your doctor's visits.

DAY	Date			Drug Name	Time pills taken		Number of pills taken		Use the space below to make notes about things you would like to tell the doctor (including unusual symptoms you experience, other medicine you have taken and anything else you think would be of interest.)
	Month	Day	Year		AM	PM	AM	PM	
1				Dabrafenib (twice daily)					
				Trametinib (once daily)					
				HCQ or placebo (twice daily)					
2				Dabrafenib (twice daily)					
				Trametinib (once daily)					
				HCQ or placebo (twice daily)					
3				Dabrafenib (twice daily)					
				Trametinib (once daily)					
				HCQ or placebo (twice daily)					
4				Dabrafenib (twice daily)					
				Trametinib (once daily)					
				HCQ or placebo (twice daily)					
5				Dabrafenib (twice daily)					
				Trametinib (once daily)					
				HCQ or placebo (twice daily)					

DAY	Date			Drug Name	Time pills taken		Number of pills taken		Use the space below to make notes about things you would like to tell the doctor (including unusual symptoms you experience, other medicine you have taken and anything else you think would be of interest.)
	Month	Day	Year		AM	PM	AM	PM	
6				Dabrafenib (twice daily)					
				Trametinib (once daily)					
				HCQ or placebo (twice daily)					
7				Dabrafenib (twice daily)					
				Trametinib (once daily)					
				HCQ or placebo (twice daily)					
8				Dabrafenib (twice daily)					

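### The trametinib reduction table lists every dose level as twice daily, so its first reduction, taken literally, raises a patient from 2 to 3 mg/day

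*Combined protocol and SAP*

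**What the plan says.** Section 5.4.1.2, Table 2, has four dose rows for trametinib. The starting dose is "2 mg twice daily" and the first reduction is "1.5 mg twice daily". The second and third reductions are 1.0 mg and 0.5 mg, also twice daily. The last row, which tells the site when to stop the drug, switches frequency: "If unable to tolerate 0.5 mg once daily".

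Elsewhere the regimen is once daily:

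- Sections 5.1.1 and 5.1.2 assign 2 mg once a day in Arms A and B.
- Section 5.1.3 gives the starting dose as 2 mg a day, taken once daily.
- Section 1.1.3, on the preceding single-arm trial: "trametinib 2 mg po qd was used for the single arm phase II study".
- Appendix III, for patients: "Trametinib should be taken once daily, on an empty stomach".

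The toxicity rules refer to dose levels and do not restate milligrams. After a grade 3 event, for example, Table 4 in Section 5.4.2 says to "restart dabrafenib and trametinib both reduced by one dose level". Similar instructions to restart trametinib at a lower level appear for rash (Table 6), pneumonitis (Table 9), ejection-fraction decrease (Table 10) and hypertension (Table 12).

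**The concern.** A patient reaches Table 2 because of toxicity. If the table's frequency is followed, the step labelled first reduction increases trametinib and the next step only returns the patient to the original dose.

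The stakes are highest where trametinib is the suspected cause. Section 5.4.1.1 names reduced ejection fraction and pneumonitis among the events for which trametinib, not dabrafenib, is modified. Section 5.4.3.6 reports ejection-fraction decreases in 9% of patients on the combination against 0% on dabrafenib alone.

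Re-escalation adds to this. Section 5.4.1.4, the second footnote to Table 6 and footnote c to Table 12 allow return to an earlier dose level. Table 2's top level, read literally, is twice the assigned dose.

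Trametinib is commercial supply (Section 8.2.10), and the central drug-request process in Section 8.3 covers only hydroxychloroquine and placebo. The documents describe no central check that would catch a wrong trametinib dose.

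**Working it through.** **Inputs.** Assigned dose: 2 mg, once a day (Sections 5.1.1, 5.1.2, 5.1.3). Dose per intake at each level: 2, 1.5, 1.0 and 0.5 mg (Section 5.4.1.2, Table 2). Intakes per day: 2 as Table 2 is written, 1 as the regimen is written. The plan gives no mg/day totals, so there is no stated total to reproduce.

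**Formulas.** Daily dose = mg per intake × intakes per day. Change from plan = daily dose ÷ 2 mg/day − 1.

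| Level | Table 2 as written | Change from 2 mg/day | Once daily | Change from 2 mg/day |
|---|---|---|---|---|
| Start | 2 × 2.0 = 4 mg/day | +100% | 2.0 mg/day | 0% |
| First reduction | 2 × 1.5 = 3 mg/day | +50% | 1.5 mg/day | −25% |
| Second reduction | 2 × 1.0 = 2 mg/day | 0% | 1.0 mg/day | −50% |
| Third reduction | 2 × 0.5 = 1 mg/day | −50% | 0.5 mg/day | −75% |

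Every written level is twice its once-daily counterpart. Of the three reductions, the first raises the dose above plan, the second leaves it at plan and only the third lowers it. The starting row is also above plan.

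**Which frequency was meant.** Three checks separate the readings:

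1. The stopping row refers to 0.5 mg once daily. No dose row lists that level as written; with once-daily wording it is exactly the third reduction.
2. Table 14 (Section 5.4.3.10), for retinal pigment epithelial detachment, lowers trametinib by 0.5 mg and stops it in patients on 1 mg a day. The once-daily ladder moves in steps of 0.5 mg/day; the written ladder moves in steps of 1 mg/day.
3. The regimen sections, the earlier trial's dose and the pill calendar all say once daily, and no section supports 4 mg/day.

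**Is it a text-extraction fault?** Four complete cells carry the same wording, and once-daily wording survives intact in the last row of Table 2 and in Table 3 of the same section. The table is current protocol text, not a description of superseded text.

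**The case against.** The strongest reply is that nobody meant 4 mg/day and few sites would act on it. Much of this is fair:

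- The rise from 2 to 3 mg/day combines the actual starting dose from Section 5.1 with the first reduction from Table 2. Within Table 2 alone the doses fall at every step: 4, 3, 2, 1 mg/day. That is correct, but patients start on 2 mg/day, so theirs is the relevant comparison.
- Many signals point the other way. The table's first row contradicts what the patient is taking, its last row says once daily, the toxicity rules ask for a reduction, and the calendar labels trametinib once daily. Tablets come as 0.5 and 2 mg (Section 5.1.3), so the written first reduction replaces one 2 mg tablet with six 0.5 mg tablets a day (3 mg ÷ 0.5 mg), which a pharmacist would probably query. This lowers the chance of a misread. It helps less at the second level, where the total is simply unchanged.
- Not every serious event uses the table. Grade 4 pneumonitis and symptomatic grade 3–4 ejection-fraction loss stop trametinib permanently (Tables 9 and 10). For these two toxicities the exposure is grade 2–3 pneumonitis and asymptomatic ejection-fraction decrease that recovers within 4 weeks.
- The missed-dose rule in Section 5.1.3 ("the dose can be taken if it is more than 12 hours until the next scheduled dose") suits once-daily dosing, but Section 8.2.13 and Appendix III say missed doses are not taken later. It is weak evidence, and the conclusion does not need it.
- The toxicity tables do not cite Table 2 by number. The link is inferred, but no other table sets out the trametinib levels.

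These points reduce the probability of harm. None makes the four cells correct, and no erratum in the documents corrects them.

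**Conclusion.** The concern holds. Table 2 contradicts the assigned regimen in four cells and contradicts itself in its last row. For a patient on 2 mg/day its three reductions come to 3, 2 and 1 mg/day instead of 1.5, 1.0 and 0.5 mg/day.

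This rests on two readings: patients start at 2 mg once daily, as both arms specify, and Table 2 is the source for the trametinib levels that the toxicity rules invoke.

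It must be fixed because of what a misread would do to a patient with toxicity, even though the consistent text elsewhere makes a misread less likely. It has no bearing on sample size, power, type I error or the validity of the primary comparison.

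**What to change.** In Section 5.4.1.2, Table 2, change the frequency in the four dose rows so that they read 2, 1.5, 1.0 and 0.5 mg once daily. Leave the last row as it is; it will then match the third reduction. Leave Table 14's rule of stopping at 1 mg a day unchanged, because Section 5.4.2 allows toxicity-specific instructions to differ from the general ones. Notify sites of the correction.

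The cost is four table cells and a site notice. No analysis, sample size or timing changes.
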